[name] is a consultant for Edwards Lifesciences and for Abbott Vascular, and his employer has research contracts from Edwards Lifesciences, Abbott Vascular, Medtronic, St Jude Medical, and Boston Scientific.

ABBREVIATIONS

ADE	Adverse device effect
AR	Aortic valve regurgitation
AS	Aortic valve stenosis
CT	Computed tomography
BASILICA	Bioprosthetic or native Aortic Scallop Intentional Laceration to prevent Iatrogenic Coronary Artery obstruction
iFR	Instantaneous wave-free Flow Reserve index
LAMPOON	Intentional Laceration of the Anterior Mitral leaflet to Prevent iatrogenic left ventricular Outflow tract ObstructiON after transcatheter mitral valve replacement
MACE	Major adverse clinical events
SADE	Serious adverse device effect
SAE	Serious adverse event
TAVR	Transcatheter aortic valve implantation
TEE	Transesophageal echocardiography
THV	Transcatheter heart valve
VARC	Valve academic research consortium (criteria)
UADE	Unanticipated adverse device effect
UP	Unanticipated problem
6MWT	Six minute walking test

KEYWORDS

Transcatheter aortic valve replacement

Valve-in-valve TAVR

Coronary artery obstruction

Bioprosthetic heart valve failure

PRÉCIS

Transcatheter aortic valve replacement (TAVR) is an option to treat aortic valve stenosis or failure of a surgically implanted tissue valve. Sometimes TAVR displaces the diseased aortic valve leaflets outwards, causing life-threatening obstruction of the coronary arteries that supply blood to the heart. This is more common in surgically implanted tissue valves that are designed to achieve the largest aortic valve orifice area. Despite attempts to protect the coronary arteries from obstruction in these patients using coronary stents, the mortality of TAVR-associated coronary artery obstruction remains prohibitively high.

The investigators have developed and tested a technique to tear the existing aortic valve leaflet and enable TAVR in such patients. The procedure is called Bioprosthetic or native Aortic Scallop Intentional Laceration to prevent Iatrogenic Coronary Artery obstruction (BASILICA).

The purpose of this study is to perform BASILICA in patients who have no good options to prevent coronary artery obstruction during TAVR.

Table of Contents

1.0	Protocol Summary	5
2.0	OBJECTIVE.....	7
3.0	BACKGROUND	7
4.0	CLINICAL AND SCIENTIFIC JUSTIFICATION.....	7
4.1	Predictors of coronary artery obstruction after TAVR.....	8
5.0	TREATMENT OPTIONS	9
6.0	STUDY DESIGN	9
6.1	Schematic of Study Design	9

1.0 Protocol Summary

Title:	Bioprosthetic or native Aortic Scallop Intentional Laceration to prevent Iatrogenic Coronary Artery obstruction (BASILICA) prospective investigation
Précis:	
Transcatheter aortic valve replacement (TAVR) is an option to treat aortic valve stenosis or failure of a surgically implanted tissue valve. Sometimes TAVR displaces the diseased aortic valve leaflets outwards, causing life-threatening obstruction of the coronary arteries that supply blood to the heart. This is more common in surgically implanted tissue valves that are designed to achieve the largest aortic valve orifice area. Despite attempts to protect the coronary arteries from obstruction in these patients using coronary stents, the mortality of TAVR-associated coronary artery obstruction remains prohibitively high.
 
The investigators have developed and tested a technique to split the existing aortic valve leaflet and enable TAVR in such patients. The procedure is called Bioprosthetic or native Aortic Scallop Intentional Laceration to prevent Iatrogenic Coronary Artery obstruction (BASILICA).
 
The purpose of this study is to perform BASILICA in patients who have no good options to prevent coronary artery obstruction during TAVR.

Hypothesis:	BASILICA avoids life-threatening coronary artery obstruction in at-risk patients during TAVR
Specific Aims	
Specific aim 1: To determine early multi-center feasibility of BASILICA
 
Specific aim 2: To determine provisional feasibility of BASILICA (Freedom from MACE to hospital discharge and 30days)

Primary Safety Endpoint	Freedom from MACE (according to VARC-2) at 30 days
Primary Feasibility End-points	Procedure clinical success (defined below)
Study Population:	Patients with bioprosthetic aortic valve failure or native aortic valve stenosis at high risk of coronary artery obstruction from leaflet displacement during TAVR

Inclusion Criteria	
Adults age \geq 21 years
 
High or extreme risk of surgical aortic valve replacement according to the local multidisciplinary heart team
 
Undergoing TAVR for valve-in-valve failure or native aortic stenosis ("on-label" TAVR)
 
Deemed likely to suffer coronary artery obstruction from TAVR according to multidisciplinary heart team
 
Concurrence of the study eligibility committee

Exclusion Criteria	
Does not consent to participate
 
Excessive target aortic leaflet calcification or masses on baseline CT
 
Survival despite successful procedure expected < 12 months
 
Subjects unwilling to participate or unwilling to return for study follow-up activities.
 
Pregnancy or intent to become pregnant prior to completion of all protocol follow-up procedures

Phase:	Pilot
Study Procedure	
NHLBI Data Coordinating Center
 
NHLBI + Local Institutional Review Boards
 
Sites are trained by national PIs and NHLBI investigators
 
Subjects are identified by site investigators
 
Baseline and follow-up CT and fluoroscopy are analyzed by core laboratory
 
Subject eligibility is confirmed by local multidisciplinary heart team including cardiac surgery, and is confirmed by study eligibility committee
 
Subjects are enrolled prospectively
 
Primary analysis based on 30-day outcomes; Secondary analysis includes 12-month outcomes

Sample Size	30 subjects at up to 6 sites
Risk-benefit determination	These patients have few or no therapeutic alternatives and have the potential to benefit from this procedure
Number of Sites enrolling participants:	6
Study Duration:	Two years
Participant Duration:	One year

2.0 OBJECTIVE

The objective of this protocol is further to characterize the feasibility and safety of Bioprosthetic or native Aortic Scallop Intentional Laceration to prevent Iatrogenic Coronary Artery obstruction (BASILICA), in patients at high risk of coronary artery obstruction complicating TAVR.

In this protocol, we use transcatheter heart valves (THV) according to their marketed indication, on-label.

3.0 BACKGROUND

Transcatheter aortic valve replacement (TAVR) is an effective alternative to surgical aortic valve replacement in intermediate and high-risk patients. TAVR is also an effective treatment for failure of bioprosthetic surgical aortic valves, a treatment known as valve-in-valve TAVR. Valve-in-valve TAVR is associated with low mortality, satisfactory hemodynamics, and good intermediate-term functional outcomes in selected high risk patients [1, 2]. Valve-in-valve TAVR commonly exacerbates valve under-sizing (a phenomenon known as patient-prosthetic mismatch), which increases one-year mortality [1, 2].

Coronary artery obstruction is a devastating complication of valve-in-valve TAVR with a greater than 50% mortality [3]. Coronary artery obstruction occurs when the transcatheter heart valve displaces the underlying surgical or native aortic valve leaflets outwards and obstructs the coronary artery ostia, usually by sealing the sinus of Valsalva at the sinotubular junction (Figure 1). Coronary artery obstruction occurs most commonly during TAVR for surgical bioprostheses designs intended to maximize effective aortic orifice area ("stented" bioprostheses that have externally mounted leaflets, and "stentless" surgical bioprostheses). Coronary artery obstruction can be predicted by pre-procedure morphology and CT.

4.0 CLINICAL AND SCIENTIFIC JUSTIFICATION

We propose a solution based on our non-clinical [5] and initial clinical [6] LAMPOON procedure (intentional catheter-based traversal and laceration a mitral valve leaflet structure in order to prevent the complications of leaflet displacement after related transcatheter mitral valve implantation). In LAMPOON, we use catheter techniques to split the mitral valve leaflet to prevent obstruction of the left ventricular outflow tract.

[figure not shown]

Figure 1. Coronary artery obstruction a

[figure not shown]

Figure 2. A represent BASILICA TAVR procedure. A: An electrified crossing wire (1) traverses the level of a bioprosthetic valve frame (2). B: The electrified shaft of the BASILICA guidewire is splitting the left coronary scallop of the intended aortic valve (3). C: After successful BASILICA, a Sapien 3 TAVR valve is implanted and coronary arteriography demonstrates patency of the left coronary artery ostium.

Using a simple modification of the LAMPOON technique, we have developed a technique to split an aortic valve leaflet, whether bioprosthetic or native, to prevent coronary artery obstruction after TAVR. The new technique is called Bioprosthetic Aortic Scallop Intentional Laceration to prevent iatrogenic Coronary Artery obstruction (BASILICA). Figure 2 shows a representative BASILICA TAVR procedure.

To date, seven patients have undergone compassionate BASILICA to enable TAVR. All survived to discharge without major adverse events.

4.1 Predictors of coronary artery obstruction after TAVR

Table 1 lists anatomic and artificial valve factors thought to contribute to the risk of coronary artery obstruction during TAVR. Many of these are continuous parameters and are thought to interact with each other, such as narrow and short sinuses of Valsalva. One of the most powerful predictors is thought to be a small “virtual tube to coronary artery distance (VTC)”, especially when less than 3-4mm[3, 7]. However, the risk determination must integrate all of these factors, and must incorporate judgement.

Table 1. Predictors of coronary artery obstruction after TAVR, expanded from Dvir [7] and Riberio[3]

Anatomic factors	Narrow virtual transcatheter heart valve to coronary distance (VTC): <4mm* Low-lying coronary ostia Narrow sinotubular junction Low sinus of Valsalva height Narrow sinuses of Valsalva * Previous root repair (eg, root graft and coronary reimplantation)
Bioprosthetic valve factors	Internal stent frame with external leaflets (eg, Mitroflow, Trifecta)* No stent frame (homograft, stentless valves)* Long or thick or bulky bioprosthetic leaflets Supra-annular position

	Stent posts that extend beyond sinotubular junction Intended overexpansion/fracture of bioprosthetic valve frame during TAVR
Transcatheter valve factors	Extended sealing cuff High implantation

[figure not shown]
* Independent predictor of coronary obstruction in one retrospective registry [3]

5.0 TREATMENT OPTIONS

Candidates for TAVR with BASILICA have no good alternative treatment options. They are not eligible for definitive treatment using surgical aortic valve repair or replacement. Despite pre-positioning of bailout coronary stent delivery systems before TAVR, the outcome of TAVR-induced coronary artery obstruction is catastrophic with a mortality > 50% [3].

6.0 STUDY DESIGN

6.1 Schematic of Study Design

6.2 Overview of Study Design

This is a prospective, open-label, single-arm, multi-center, investigator-initiated, independently-adjudicated trial of BASILICA immediately before TAVR in subjects at high risk of coronary artery obstruction.

Candidates will be identified by the participating structural heart disease programs. In evaluation of aortic valve disease, candidates will undergo clinical evaluation, echocardiography, and contrast-enhanced gated cardiac CT. Eligibility will be reviewed and proposed by the local multidisciplinary heart teams. Candidates will then undergo central eligibility review by the sponsor and designated investigators. If deemed eligible, candidates will be offered participation in the study.

Once enrolled, subjects will undergo baseline assessment and blood tests.

Subjects will be admitted to the hospital and undergo TAVR with BASILICA. They will undergo endpoint assessment before discharge, after 30 days, and then 12 months.

6.3 Study Population

Subjects are undergoing planned TAVR because of high or prohibitive risk of surgical aortic valve replacement for bioprosthetic aortic valve failure or native aortic valve stenosis. The subjects are deemed to have excessive risk of TAVR-induced coronary artery obstruction based on features enumerated in Table 1 in section 4.1.

6.4 BASILICA TAVR Procedure

The BASILICA TAVR procedure is planned from a contrast-enhanced CT of the heart to select a suitable transcatheter heart valve size, predict suitability of the sub- and supra-annular landing zone, and predict post-TAVR coronary obstruction related leaflet encroachment on the sinotubular junction and coronary artery ostia. Knowledge of the aortic valve operative history is integrated into this assessment. These data are used to select a BASILICA traversal point, radiographic landmarks, and fluoroscopic projection angles.

The procedure is performed under general anesthesia or under moderate sedation at the discretion of the institutional heart team. The BASILICA procedure has three steps: (1) leaflet traversal with a guidewire, followed by (2) leaflet laceration, immediately followed by (3) TAVR. These are all guided by fluoroscopy and adjunctive echocardiography as needed.

Research study participation is defined as beginning the moment BASILICA traversal is attempted.

First catheter access is obtained typically via four arterial introducer sheaths (two for BASILICA, one for hemodynamics and angiography, and one for TAVR) and at least one venous introducer sheaths for temporary transvenous pacing. Anticoagulation with heparin or equivalent achieves an activated clotting time > 300s.

Hemodynamic and echocardiography measurements are recorded at baseline including gradients across the aortic valve, severity of valvular obstruction and severity of valvular regurgitation.

Two retrograde catheters are positioned, using a guidewire anchor as needed, in the LVOT and Aorta respectively. Care is taken to avoid entrapment of mitral valvular structures. A snare catheter is positioned in the LVOT. A coaxial traversal guiding catheter system (typically tandem catheters) directs electrosurgery devices (typically a rigid 0.014" guidewire inside a polymer jacket wire convertor) against the base of the coronary cusp targeted for laceration, using fluoroscopic and/or echocardiographic guidance.

Traversal is accomplished by transcatheter electrosurgery by connecting the back end of the 0.014" guidewire to an electrosurgery pencil during short bursts of "pure, cutting" radiofrequency energy at approximately 30W. The guidewire is repositioned as needed until it crosses the aortic leaflet and is snare-retrieved and externalized. Nonionic conductive flush (dextrose 5%) can be administered as needed via the guiding catheters to reduce guidewire char and thromboembolism.

Next the polymer jacket wire convertor is withdrawn, and the traversal wire is modified by the operator by (1) denuding a non-circumferential segment ~2mm in length, 90° arc and (2) kinking the denuded segment to enforce its position at the inner curvature of the intended guidewire lacerating surface. Next the polymer jacket radiopaque marker tip is locked adjacent to the kinked denuded shaft segment. Next the en-snared guidewire is externalized to position the lacerating surface across the base of the leaflet.

BASILICA may be performed on one or two valve leaflets that may threaten coronary artery obstruction.

Next, at operator discretion, the transcatheter heart valve may be positioned before or after the laceration step. If before, the operator assures no entrapment of the TAVR system with the laceration system of catheters.

At operator discretion, stroke prevention strategies may be employed, including external carotid artery compression and intravascular embolic protection devices.

Laceration is performed by positioning the laceration surface along the intended leaflet base, and applying tension on both free ends of the guidewire while simultaneously apply electrosurgery energy (typically 70W) in short bursts, until the laceration is complete and the guidewire is free.

Hemodynamics are recorded quickly after laceration before TAVR. Coronary artery stent systems are positioned prophylactically at the discretion of the operator. Predilatation, including intentional disruption of the bioprosthetic valve frame, is performed at operator discretion, before or after TAVR. Then TAVR is performed using established techniques typically during rapid ventricular pacing. The device size and inflation volumes are selected and applied at the discretion of the operator. Post-dilatation is performed at operator discretion to achieve an optimum TAVR result. Coronary artery patency is established using angiography and, if employed, using prepositioned pressure-tip guidewires. Coronary artery pressure (instantaneous wave-free ratio, *iFR*) may further be examined if possible at the discretion of the operator.

Completion hemodynamics and echocardiography are recorded. Finally, percutaneous femoral artery and vein vascular hemostasis is obtained and the subject convalesces in the appropriate inpatient recovery unit.

Before discharge, follow-up transthoracic echocardiography is recorded. A single contrast-enhanced CT of the heart is obtained before discharge if renal function allows, otherwise it is deferred as long as 30-days. Blood tests are recorded for research only as obtained for medical care.

Anticoagulation and antiplatelet therapy is prescribed after discharge at the physicians' discretion, and is recorded.

All subjects are to be enrolled in the TVT-Registry postmarketing TAVR registry.

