6.5 Time and Events Schedule

	Screening	Baseline	Day 0	Inpatient	30 d (\pm 14d) FU	12 mo (\pm 4 wk) (transcatheter)
Baseline informed consent:		X				
Multidisciplinary heart team eligibility determination		X				

	Screening	Baseline	Inpatient	Day 0	30 d (± 14 d) FU	12 mo (± 4 wk) (range) ELL
Baseline clinical assessment		X				
NYHA Classification		X				X
Blood tests: CBC, Platelet, Haptoglobin, Liver panel, Chemistry Panel, Albumin, LDH, BNP/Pro-BNP, Troponin that are obtained for medical care are captured for research. Pregnancy test if applicable before day 0 and before research CT		X	X		X	X
Vital signs and in-person visit		X			X	X
Cardiac CT contrast-enhanced gated dynamic	Screening or baseline	Screening or baseline	Inpatient or 30D		Inpatient or 30D	
BASILICA assisted TAVR Enrollment begins once attempted			X			
Echocardiogram, surface or transesophageal	Screening or baseline	Screening or baseline	X		X	X
Adverse event assessment			X X		X	X
Data capture from TVT-registry surveillance: KCCQ-12, baseline-only frailty		X			X	X

Subjects would receive continuing care from their primary physicians with consultant input as requested from the structural heart disease program.

For subjects who die, necropsy evaluation is requested to examine the heart at NIH.

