6.6 Visit Schedule

[figure not shown]
All activities except TAVR/BASILICA, Consent, KCCQ, and Adverse event assessment are performed for standard clinical care.

Timing	Event
Screening (any time)	Medical, Surgical and Interventional Assessment, determination and documentation that the subject has no other options for TAVR
Screening (any time)	Cardiac CT contrast enhanced, gated dynamic
Screening (any time)	Echocardiogram, transesophageal or surface
Screening (any time)	Multidisciplinary heart team eligibility determination and documentation
Baseline (within 30 days of procedure)	Research Informed Consent to include documented Inclusion and Exclusion criteria

Baseline (within 30 days of procedure)	
Clinical Assessment to include:
 
 • Vital signs • Baseline symptoms • NYHA Classification • Other co-morbidities that could preclude the subject living the required 12 months post procedure • Surface echocardiogram-transthoracic and/or transesophageal • TVTRegistry quality surveillance data, including QOL, Frailty 
Clinical Blood tests if obtained are captured for research
 
 • CBC • Platelets • Haptoglobin • Liver Function panel • Chemistry panel • Troponin • Albumin • LDH • BNP/Pro-BNP • Pregnancy test if applicable
Day 0	
TAVR with BASILICA procedure attempted, which marks enrollment.
 
Subjects who do not proceed to BASILICA attempts are recorded as screen failures, and the reason is recorded.

Pre-discharge	
Clinical Evaluation to include:
 
 • Cardiac CT scan contrast enhance, gated dynamic- if not clinically suitable then re-schedule for 30 Day follow up visit • Surface echocardiogram and/or transesophageal • Adverse Event Assessment 
Clinical Blood tests if obtained are captured for research
 
 • CBC • Platelets • Haptoglobin • Liver Function panel • Chemistry panel • Troponin • Albumin • LDH • BNP/Pro-BNP 
Pregnancy test if applicable

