10.0 BIOSTATISTICAL AND ANALYTICAL CONSIDERATIONS

10.1 Sample Size

The sample size is not statistically derived. This is a safety and feasibility study that enables patient access to a novel medical procedure, when these patients have no other good medical options to treat symptomatic aortic valve failure.

Up to 60 subjects will be consented until 30 subjects undergo attempted BASILICA TAVR in this protocol.

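### A procedure abandoned because BASILICA equipment could not be placed can become a screen failure and leave the primary-endpoint denominator, although that endpoint requires successful access and delivery

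*Combined protocol and SAP*

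**What the plan says.** All references are to the combined protocol and SAP.

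- **Start of participation (6.4).** "Research study participation is defined as beginning the moment BASILICA traversal is attempted". The same section sets out the procedure: "The BASILICA procedure has three steps: (1) leaflet traversal with a guidewire, followed by (2) leaflet laceration, immediately followed by (3) TAVR".
- **What comes before traversal (6.4).** "First catheter access is obtained typically via four arterial introducer sheaths (two for BASILICA", with the others for haemodynamics and for TAVR. Two retrograde catheters, a snare in the outflow tract and a coaxial guiding system are then positioned. Electrosurgical traversal is described only after that.
- **Enrolment.** The table in 6.5 has "BASILICA assisted TAVR Enrollment begins once attempted". Section 6.6 has "TAVR with BASILICA procedure attempted, which marks enrollment", and adds: "Subjects who do not proceed to BASILICA attempts are recorded as screen failures, and the reason is recorded". Section 6.2 uses the word earlier in the sequence: "Once enrolled, subjects will undergo baseline assessment and blood tests".
- **Sample size (10.1).** "Up to 60 subjects will be consented until 30 subjects undergo attempted BASILICA TAVR in this protocol".
- **Primary feasibility endpoint (10.2.1).** Clinical success is judged at exit from the catheterization laboratory. One required item is that the BASILICA system is successfully introduced, delivered and retrieved.
- **Adverse device effects (11.1).** Being unable to position catheters or guidewires is listed under BASILICA procedure failure, beside failure to traverse and failure to lacerate.
- **Analysis sets.** Section 10.2 names none. Section 10.2.2 defines 30-day MACE without a denominator. The stopping rules in 10.3.2 and 10.3.3 count subjects in the stratum and deaths within 30 days after the procedure.

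**The concern.** The endpoint and the entry rule do not fit together. The endpoint treats failure to get BASILICA equipment into place as a failure of the technique. The entry rule lets a subject with exactly that failure leave the study before being counted, if the team stops before attempting traversal.

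Feasibility is the first specific aim, and the primary result is a descriptive proportion out of about 30. An omission of this kind removes a failure and never a success, so its effect on that proportion runs in one direction only. The plan also specifies no 30-day follow-up for such subjects, so their later outcomes could go unreported.

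Separately, no sentence says which subjects form the denominator for 30-day MACE or for the stopping counts. In strata this small, one subject can decide whether a boundary is met, so the set should be named before the first death.

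**Working it through.** **1. The path of one abandoned case.** The BASILICA sheaths are placed on Day 0, but the catheters or snare cannot be positioned and the team stops.

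- Under 6.4, traversal was not attempted, so participation has not begun.
- Under 6.6, with traversal as the first step of BASILICA, the subject did not reach an attempt and is a screen failure.
- Under 10.1, the subject is not one of the 30.
- Under 10.2.1, the same event would fail the access and delivery item.
- Under 11.1, it is a BASILICA procedure failure.

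**2. Effect on the primary proportion.** The documents give no rate of abandonment before traversal, so all counts here are assumed. With *s* successes among 30 traversal-attempted subjects, counting one omitted failure changes the proportion by s/30 − s/31 = s/930.

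- s = 24: 24/930 = 2.6 points
- s = 28: 28/930 = 3.0 points
- s = 30: 30/930 = 3.2 points

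Example with exact (Clopper-Pearson) 95% intervals:

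| Omitted failures counted | Success | 95% CI |
|---|---|---|
| 0 | 28/30 = 93.3% | 77.9 to 99.2 |
| 1 | 28/31 = 90.3% | 74.2 to 98.0 |
| 2 | 28/32 = 87.5% | 71.0 to 96.5 |

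Each shift lies inside the sampling interval.

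**3. 30-day MACE.** Here the direction is not fixed. From an assumed 24/30 = 80.0% MACE-free, adding an abandoned subject without an event gives 25/31 = 80.6%. Adding one with an event gives 24/31 = 77.4%.

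**4. Stopping rules.** First, the plan's own figures. For each n, take the smallest number of deaths d with P(p > p0) ≥ 0.90 under Beta(a + d, b + n − d). The inputs are p0 = 0.15, a = 0.9, b = 5.1 (10.3.2) and p0 = 0.20, a = 1.2, b = 4.8 (10.3.3). This reproduces every row of both boundary tables. An exact calculation against the 10.3.2 boundary gives a 17.5% stopping probability at 15% true mortality; the plan's simulation gives 17.3%. The rules are arithmetically sound.

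Next, sensitivity to one subject:

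| Stratum | Count | Posterior | Result |
|---|---|---|---|
| No overexpansion | 3 deaths in 6 | 0.921 | stop |
| Same, one pre-traversal death left out | 2 in 5 | 0.799 | continue |
| Same, one pre-traversal survivor added | 3 in 7 | 0.896 | continue |
| Overexpansion | 3 deaths in 5 | 0.904 | stop |
| Same, one pre-traversal survivor added | 3 in 6 | 0.869 | continue |

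Leaving out a death makes stopping less likely, and so does adding a survivor. Widening the stopping set to include pre-traversal subjects is therefore not automatically the safer choice.

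**The case against.** The strongest case on the other side has five parts.

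- **The sections agree.** A reader might infer that the enrolment triggers contradict one another. They need not. Section 6.4 gives an express definition and makes traversal the first step of BASILICA, so *attempted* in 6.5, 6.6 and 10.1 can be read as traversal attempted. Only 6.2 is out of line, and *enrolled* there may be loose for *consented*. This stands. But the consistent reading is the one that produces the omission, so it does not answer the point.
- **The endpoint item keeps its content.** A reader might infer that access and delivery can never fail once traversal defines entry. That goes too far: the wire is still snared and externalized, the lacerating surface is still positioned, a second leaflet may be treated, and equipment must be retrieved. An access injury in a subject who goes on to attempted traversal is also counted. Only abandonment before traversal is lost.
- **The start point is a legitimate choice.** Section 13.1.1 describes traversal as the guidewire's first use, so starting there is defensible. It suits the enrolment target and the safety counts, but not an endpoint that scores earlier steps.
- **The sets are partly implied.** Section 10.1 fixes 30 attempted subjects, and the stopping tables and simulations run to 30. This points to the attempted set, though no sentence assigns it.
- **The consequence is small.** The study is descriptive, with no success threshold or test. At 15% true mortality, 3 or more deaths in 6 has a probability of about 5%, before any abandoned case is also assumed. Recorded screen-failure reasons (6.6), adverse-event recording from Day 0 (11.2.3), death reporting (11.2.4), independent review of deaths (10.2.5) and DSMB review (10.3) give some visibility, although the plan does not say whether they all reach screen failures. None of them defines a denominator.

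One further caution stands. Some procedures stop before traversal for reasons unrelated to BASILICA, and scoring those as failures would be unfair to the technique.

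**Conclusion.** The point holds in a limited form. Followed as written, sections 6.4 and 6.6 allow a procedure that failed at BASILICA access, delivery or positioning to be recorded as a screen failure and to leave the denominator of an endpoint that scores those steps. Each such case raises the reported success proportion by 2.6 to 3.2 points for success counts of 24 to 30 out of 30, always in favour of BASILICA.

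This rests on two assumptions: that *attempted* means traversal attempted, and that at least one such case occurs. The documents give no rate, and the number may be zero. The ceiling of 60 consents in 10.1 is a limit, not a forecast of abandoned cases.

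A reader might also infer that the safety endpoint or the stopping rules are biased towards BASILICA. The documents do not support that: the direction depends on the omitted subject's outcome. What is missing there is only a statement of which subjects count.

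**What to change.** 1. State in 6.5, 6.6 and 10.1 that *attempted* has the meaning given in 6.4. In 6.2, write *consented* if that is meant.
2. Keep the 30 traversal-attempted subjects as the enrolment target. Name them in 10.2.2, 10.3.2 and 10.3.3 as the set for 30-day MACE and for the stopping counts.
3. For the primary feasibility endpoint in 10.2.1, add subjects in whom placement of sheaths or catheters for BASILICA was begun on Day 0 and the procedure was abandoned before traversal because BASILICA access, delivery or positioning failed, or because of a complication of it. Count them as failures, and report the traversal-attempted proportion beside this result.
4. List pre-traversal abandonments for unrelated reasons separately, with the reason.
5. Follow all pre-traversal abandonments to 30 days and report any death among them to the DSMB individually. Do not evaluate the boundary a second time with these subjects added: the operating characteristics in 10.3 describe one series, and two evaluations would leave open which one governs.

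The cost is wording in these sections, follow-up of a few subjects who have already consented, and possibly a slightly lower reported success rate. Deciding whether a stop was BASILICA-related takes some judgement.
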